7.1. Serum Pharmacokinetics Samples

Blood samples will be collected for assessment of serum concentrations of AL001. All serum PK samples should be drawn from the arm that is not used for the infusion on day of study drug administration. Specific information on PK sample collection, processing, storage, and shipment will be provided in a separate manual. Serum PK samples for AL001 will be collected at predose and at the end of infusion (within 15 minutes after the end of infusion) on weeks 1, 2, 5, 9, 13, 17, 21, 25, 29, 33, 37, 41, 45, 49, 53, 61 (3h post EOI and 24h also), 73, 85, 97, and 105 or study completion/ET for all participants.

Serum concentration and time deviation data at each study visit/timepoint will be presented in data listings by cohort (aFTD-GRN, FTD-GRN, FTD-C9orf72) at baseline in the Safety population. Serum concentration data will be summarized by study visit/timepoint and cohort at baseline for the PK analysis population using descriptive statistics: number of participants with non-missing data (n), mean, SD, CV, median, minimum, maximum, geometric mean, and geometric CV. All serum concentration values below the limit of quantification (BLQ) will be set to zero when calculating summary statistics.

Mean serum concentration versus nominal time profiles will be plotted on both linear and semilogarithmic scales for the PK analysis population by cohort at baseline. Individual serum concentration versus actual time profiles will be plotted on both linear and semilogarithmic scales for the Safety population.

7.2. CSF Pharmacokinetic Samples

Cerebrospinal fluid (CSF) samples will be collected via lumbar puncture prior to study drug administration (if applicable) at Screening, Week 25, Week 49, and Week 97 (or the EOT/EOS Visit) to evaluate CSF PK in Part 1 only. The Week 25 lumbar puncture may be adjusted as determined by Alector's review of exploratory PD biomarkers.

CSF concentration and time deviation data will be presented in data listings by study visit and cohort in the Safety population. CSF concentration data will be summarized by study visit and cohort for the PK population using descriptive statistics: number of participants with non-missing data (n), mean, SD, CV, median, minimum, maximum, geometric mean, and geometric CV. All CSF concentration values that are BLQ will be set to zero when calculating summary statistics.

Mean CSF concentration versus nominal time profiles will be plotted on linear scale and semilogarithmic scales for the PK population by cohort at baseline. Individual CSF concentration versus actual time profiles will be plotted on linear scale and semilogarithmic scales for the Safety population.

7.3. Serum Pharmacokinetic Parameters

The individual serum concentration versus actual time data for AL001 will be used to derive the following PK parameters if data permit, by standard noncompartmental methods using Phoenix® WinNonlin® Version 8.3 or higher (Certara USA, Inc., Princeton, NJ, USA).

Parameter	Description
C_{\max}	Observed maximum serum concentration
C_{trough}	Trough serum concentration following each dose (equivalent to the trough concentration prior to each dose)
ARC_{trough}	Accumulation ratio using C_{trough} : calculated as C_{trough} for Week 61/Day 1

For the calculation of PK parameters, all serum concentrations that are BLQ prior to the first measurable concentration will be set to zero and treated as missing thereafter.

PK parameters will be summarized for the PK population by cohort in tables using the following descriptive statistics: n, arithmetic mean, SD, CV, geometric mean, geometric mean CV, 90% CI, minimum, median, and maximum. Individual PK parameters will be presented in data listings for the PK population.

Description of any needed population PK analysis will be provided in a separate analysis plan.

8. Pharmacodynamic Biomarkers

PD endpoints will be described and summarized by cohort at baseline and each timepoint, as will the percent change from baseline for each PD endpoint. PGRN will be evaluated in plasma and CSF samples.

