- ^t A Part 1 EOT visit will be completed by participants who discontinue study drug but remain in the study and continue to perform assessments. Part 1 EOT assessments should be completed as soon as possible after the decision is made. A Part 1 EOS visit will be completed by participants who discontinue study drug and all assessments. Part 1 EOS assessments should be completed as soon as possible after the decision is made.

Table 6: Schedule of Pharmacokinetic, Immunogenicity, and Pharmacodynamic Biomarker Sample and Imaging Assessments – Part 1, Treatment Period

Timepoint	Vital Signs	Serum PK sample ^a	TriPLICATE ECG	Serum ADA sample	Progranulin plasma sample	Exploratory plasma PD biomarker samples ^b	Whole blood for WBC	Exploratory whole blood PD biomarker samples ^c
Screening	X		X					
V1 (Week 1): Pre-dose	X	X	X	X	X	X	X	X
V1 (Week 1): End of infusion	X	X	X					
V2 (Week 2)	X	X		X	X	X	X	X
V3 (Week 5): Pre-dose	X	X		X	X	X	X	
V3 (Week 5): End of infusion	X	X						
V4 (Week 9): Pre-dose	X	X		X	X	X	X	
V4 (Week 9): End of infusion	X	X						
V5 (Week 13): Pre-dose	X	X		X	X	X	X	X
V5 (Week 13): End of infusion	X	X						
V6 (Week 17): Pre-dose	X	X		X	X	X	X	
V6 (Week 17): End of infusion	X	X						
V7 (Week 21): Pre-dose	X	X		X	X	X	X	
V7 (Week 21): End of infusion	X	X						
V8 (Week 25): Pre-dose	X	X	X	X	X	X	X	X
V8 (Week 25): End of infusion	X	X	X					
V9 (Week 29): Pre-dose	X	X		X	X	X	X	
V9 (Week 29): End of infusion	X	X						
V10 (Week 33): Pre-dose	X	X		X	X	X	X	
V10 (Week 33): End of infusion	X	X						
V11 (Week 37): Pre-dose	X	X		X	X	X	X	X
V11 (Week 37): End of infusion	X	X						
V12 (Week 41): Pre-dose	X	X		X	X	X	X	
V12 (Week 41): End of infusion	X	X						
V13 (Week 45): Pre-dose	X	X		X	X	X	X	
V13 (Week 45): End of infusion	X	X						
V14 (Week 49): Pre-dose	X	X	X	X	X	X	X	X
V14 (Week 49): End of infusion	X	X	X					
V15 (Week 53): Pre-dose	X	X		X	X	X	X	

Timepoint	Vital Signs	Serum PK sample ^a	Triuplicate ECG	Serum ADA sample	Progranulin plasma sample	Exploratory plasma PD biomarker samples ^b	Whole blood for WBC	Exploratory whole blood PD biomarker samples ^c
V15 (Week 53): End of infusion	x	x						
V16 (Week 57): Pre-dose	x							
V16 (Week 57): End of infusion	x							
V17 (Week 61): Pre-dose	x	x		x	x	x	x	x
V17 (Week 61): End of infusion	x	x						
V17 (Week 61): 3 hr ± 90 minutes post end of infusion		x						
V17A (Week 61): The next day after V17		x			x			
V18 (Week 65): Pre-dose	x							
V18 (Week 65): End of infusion	x							

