Timepoint	Vital Signs	Serum PK sample ^a	TriPLICATE ECG	Serum ADA sample	Progranulin plasma sample	Exploratory plasma PD biomarker samples ^b	Whole blood for WBC	Exploratory whole blood PD biomarker samples ^c
Screening	x		x					
V1 (Week 1): Predose	x	x	x	x	x	x	x	x
V1 (Week 1): End of infusion	x	x	x					
V2 (Week 2)	x	x		x	x	x	x	x
V3 (Week 5): Predose	x	x			x	x	x	
V3 (Week 5): End of infusion	x	x						
V4 (Week 9): Predose	x	x			x	x	x	
V4 (Week 9): End of infusion	x	x						
V5 (Week 13): Predose	x	x		x	x	x	x	x
V5 (Week 13): End of infusion	x	x						
V6 (Week 17): Predose	x	x			x	x	x	
V6 (Week 17): End of infusion	x	x						
V7 (Week 21): Predose	x	x			x	x	x	
V7 (Week 21): End of infusion	x	x						
V8 (Week 25): Predose	x	x	x	x	x	x	x	x
V8 (Week 25): End of infusion	x	x	x					
V9 (Week 29): Predose	x	x			x	x	x	
V9 (Week 29): End of infusion	x	x						
V10 (Week 33): Predose	x	x			x	x	x	
V10 (Week 33): End of infusion	x	x						
V11 (Week 37): Predose	x	x		x	x	x	x	x
V11 (Week 37): End of infusion	x	x						
V12 (Week 41): Predose	x	x			x	x	x	
V12 (Week 41): End of infusion	x	x						
V13 (Week 45): Predose	x	x			x	x	x	
V13 (Week 45): End of infusion	x	x						
V14 (Week 49): Predose	x	x	x	x	x	x	x	x
V14 (Week 49): End of infusion	x	x	x					
V15 (Week 53): Predose	x	x		x	x	x	x	
V15 (Week 53): End of infusion	x	x						
V16 (Week 57): Predose	x							

Timepoint	Vital Signs	Serum PK sample ^a	TriPLICATE ECG	Serum ADA sample	Progranulin plasma sample	Exploratory plasma PD biomarker samples ^b	Whole blood for WBC	Exploratory whole blood PD biomarker samples ^c
V16 (Week 57): End of infusion	x							
V17 (Week 61): Predose	x	x						
V17 (Week 61): End of infusion	x	x		x	x	x	x	x
V17 (Week 61): 3 hr ± 90 minutes post end of infusion		x						
V17A (Week 61): The next day after V17		x			x			
V18 (Week 65): Predose	x							
V18 (Week 65): End of infusion	x							
V19 (Week 69): Predose	x							
V19 (Week 69): End of infusion	x							
V20 (Week 73): Predose	x	x	x	x	x	x	x	x
V20 (Week 73): End of infusion	x	x	x					
V21 (Week 77): Predose	x							
V21 (Week 77): End of infusion	x							
V22 (Week 81): Predose	x							
V22 (Week 81): End of infusion	x							
V23 (Week 85): Predose	x	x		x	x	x	x	x
V23 (Week 85): End of infusion	x	x						
V24 (Week 89): Predose	x							
V24 (Week 89): End of infusion	x							
V25 (Week 93): Predose	x							
V25 (Week 93): End of infusion	x							
V26 (Week 97): Predose	x	x	x	x	x	x	x	x
V26 (Week 97): End of infusion	x	x	x					

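### SAP 7.3: the accumulation ratio ARCtrough has no planned value under either trough definition applied consistently, because its two samples are not named

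*SAP*

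**What the plan says.** SAP 7.3 lists three serum PK parameters, to be derived by noncompartmental methods if data permit: Cmax, Ctrough and ARCtrough.

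- **Ctrough:** "Trough serum concentration following each dose (equivalent to the trough concentration prior to each dose".
- **ARCtrough:** an accumulation ratio, calculated as Ctrough "for Week 61/Day 1".
- **Values below the limit of quantification (BLQ):** for PK parameters, "all serum concentrations that are BLQ prior to the first measurable concentration will be set to zero and treated as missing thereafter".
- **Reporting:** parameters are summarized by cohort, including the geometric mean and a 90% CI.

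The serum sampling list in SAP 7.1 ends "45, 49, 53, 61 (3h post EOI and 24h also), 73, 85, 97, and 105". It has no Week 65. In SAP Appendix 14.3 the row "V18 (Week 65): Predose" is marked for vital signs only, and so is the row "V18 (Week 65): Pre-dose" in Protocol Table 6. The rows "V3 (Week 5): Predose" and "V17 (Week 61): Predose" in SAP Appendix 14.3 both carry a serum PK sample.

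**The concern.** The trough following a dose and the trough prior to a dose are the same quantity only after a shift of one dose: the trough after dose n is the pre-dose value of dose n+1. Attached to one visit label, they are different samples. The shift occurs at every visit. It breaks the ratio because the first dose has no preceding trough in this study, and because the dose after Week 61 has no PK sample.

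At stake is whether ARCtrough can be reported as specified. SAP section 1 presents its analyses as fixed before database lock. Here the choice of denominator would be left to whoever programs the table.

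**Working it through.** The plan states no value for this ratio, so there is no figure to reproduce. The check matches dose weeks to sampling weeks.

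**Dose weeks** (Protocol 5.1: Day 1, then every 4 weeks, 25 doses). Dose i+1 falls at Week 1 + 4i, for i = 0 to 24. The last dose is at 1 + 4×24 = Week 97. Week 61 = 1 + 4×15 is the 16th dose, so its pre-dose sample follows 15 doses, the last at Week 57. The next dose is at Week 65.

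**Pre-dose serum PK weeks in Part 1** (SAP Appendix 14.3, Protocol Table 6): 1, 5, 9, 13, 17, 21, 25, 29, 33, 37, 41, 45, 49, 53, 61, 73, 85, 97. The first pre-dose PK sample after the Week 61 dose is at Week 73, after two further doses (Weeks 65 and 69).

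**The formula under each reading:**

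| Reading | Numerator | Denominator | Result |
|---|---|---|---|
| Prior to dose, both terms | Week 61 pre-dose: scheduled | Day 1 pre-dose: BLQ, set to 0, if new to AL001 | x/0, undefined |
| Following dose, both terms | Week 65 pre-dose: not scheduled | Week 5 pre-dose: scheduled | missing for everyone |
| Visit label, not a quotient | Week 61 trough | none | not a ratio |
| Prior for Week 61, following for Day 1 | Week 61 pre-dose: scheduled | Week 5 pre-dose: scheduled | computable, but not stated |

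**Reach of the zero denominator.** Protocol 1.2.2.1 reports 6 asymptomatic and 8 symptomatic GRN carriers in Study AL001-1, so at most 6 + 8 = 14 participants can have had AL001 before. At full enrolment (20 GRN plus 20 C9orf72), at least 40 − 14 = 26 participants are new to the drug, or 26/40 = 65%. Under the following-dose reading all 40 lack a planned numerator.

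**Does the numerator need Week 65?** The documents give no half-life. As an illustration only, assume a one-compartment linear model with k = ln 2 / half-life. The trough after n doses divided by the trough after one dose is then

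AR(n) = (1 − exp(−28nk)) / (1 − exp(−28k)).

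| Assumed half-life (days) | Week 61 / Week 5 pre-dose, n = 15 | Week 65 / Week 5 pre-dose, n = 16 |
|---|---|---|
| 3 | 1.002 | 1.002 |
| 5 | 1.021 | 1.021 |
| 7 | 1.067 | 1.067 |
| 10 | 1.168 | 1.168 |
| 14 | 1.333 | 1.333 |
| 21 | 1.658 | 1.658 |

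Across this range the missing Week 65 sample costs nothing: the Week 61 pre-dose value gives the same ratio to three decimals. The same shift in the denominator does matter, since it replaces the Week 5 trough with zero.

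**The case against.** The best defence is that nothing obliges a reader to use one definition for both terms. The lead definition gives the Week 5 pre-dose sample for Day 1, and the bracketed one gives the Week 61 pre-dose sample for Week 61. Both are scheduled, and a pharmacokineticist would probably choose them. This part stands: usable samples exist, and the repair is to name them. It does not rescue the text, because the SAP never states that mix and each definition fails when followed throughout. The if-data-permit clause does not help either, since the schedule and the BLQ rule exclude both consistent readings before any data arrive.

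It is also fair to say that the consequence is small. A zero denominator would show up in programming and would not pass as a plausible number. SAP 7.1 summarizes serum concentrations by visit and lists them individually, so the Week 5 and Week 61 values will be reported anyway. ARCtrough is not among the listed secondary endpoints (Cmax, Ctrough and AUCss in Table 1 of both documents).

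A reader might infer three stronger things that the documents do not support:

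- **That accumulation cannot be assessed at all.** It can, from scheduled samples, once they are named.
- **That the cumulative-exposure part of the primary endpoint is damaged.** That evaluation is by dose, for example by tertiles of the weight-normalized dose actually received. It does not use this ratio.
- **That participants from AL001-1 carry residual drug into the Day 1 sample and so produce inflated ratios.** This is possible: exclusion criteria 23 and 25 exempt AL001-1, and no washout from it is stated. But the documents give no half-life, no quantification limit for the serum assay and no actual gap between the studies, so the frequency is unknown.

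**Conclusion.** The point holds: wrong as written, minor. The formula fails when either trough definition is applied to both terms. Under the before-dose definition it is undefined for every participant new to AL001, at least 26 of 40 at full enrolment. Under the following-dose definition it has no planned numerator for anyone. An unplanned draw near Week 65, at an end-of-treatment visit or after an infusion reaction, could supply a value in isolated cases but not a planned parameter.

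This rests on three assumptions: that the ARCtrough entry in SAP 7.3 is complete as it stands, that a participant never exposed to AL001 has a BLQ value before the first dose, and, for the count of 26, full enrolment with all 14 eligible AL001-1 carriers rolling over.

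One descriptive PK parameter is affected. The primary safety objective and the sample-size statement are untouched, and no data are lost.

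**What to change.** In SAP 7.3:

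1. Define ARCtrough as the Week 61 pre-dose serum concentration divided by the Week 5 pre-dose serum concentration, the latter being the trough after the first dose.
2. Define Ctrough throughout as the pre-dose sample at the end of the preceding dosing interval, and delete the statement of equivalence. Day 1 then has no Ctrough.
3. Flag any AL001-1 participant with a quantifiable Day 1 pre-dose value, and state how that participant's ratio is handled. Decide this from exposure history and not from enrolment category, because an AL001-1 participant who has become symptomatic is screened under Category 3.

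The existing BLQ rule then works without change: once a measurable concentration has been recorded after the first dose, a BLQ value at Week 5 is treated as missing, so the ratio is missing and never divided by zero.

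The cost is a few lines of SAP text. No samples, visits or assays are added.

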1.1. Objectives and Endpoints

Table 1: Part 1 (Treatment Period): Study Objectives and Endpoints

	Objective(s)	Endpoint(s)
Primary	The primary objective of the treatment period of the study is to evaluate the safety and tolerability of IV administration of AL001 over 96 weeks in asymptomatic and symptomatic carriers of a GRN mutation causative of FTD and in symptomatic carriers of a C9orf72 mutation causative of FTD.	Primary Safety Endpoints: To assess the potential effect of cumulative exposure on the safety profile of AL001, the following will be evaluated by dose, such as by using tertiles of the actual dose (normalized to weight) received: 
• Incidence, nature, and severity of AEs and SAEs• Incidence of treatment discontinuations and study discontinuations due to AEs• Physical examination abnormalities• Neurological examination abnormalities• Changes in vital signs from baseline over time• Changes in ECGs from baseline over time• MRI abnormalities after dosing relative to baseline• Changes in clinical laboratory tests from baseline over time• Sheehan Suicidality Tracking Scale (Sheehan-STS)• Incidence of ADAs to AL001
Secondary	The secondary objectives of the treatment period of the	

	
study are to evaluate the effect of IV administration of AL001 over 96 weeks in asymptomatic and symptomatic carriers of a GRN mutation causative of FTD and in symptomatic carriers of a C9orf72 mutation causative of FTD on the following:
	
	
Secondary PK Objective:
 
 • PK 	
Secondary PK Endpoints:
 
 • Serum concentration of AL001 at specified time points • AL001 PK parameters (if data permit) ◦ C_{max} ◦ C_{trough} ◦ AUC_{ss}
	
Secondary PD Biomarker Objectives:
 
 • Longitudinal plasma and CSF PGRN concentration levels • Longitudinal levels of Sortilin in WBCs 	
Secondary PD Biomarker Endpoints:
 
 • The overall change from baseline in PGRN in CSF • The overall change from baseline in PGRN in plasma • The overall change from baseline in Sortilin in WBCs in plasma

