8.1. Progranulin Plasma Samples

Blood samples will be collected for evaluation of levels of PGRN in plasma.

PGRN plasma samples will be collected prior to study drug administration on weeks 1, 2, 5, 9, 13, 17, 21, 25, 29, 33, 37, 41, 45, 49, 53, 61 (24 h also), 73, 85, 97, and 105 or study completion/ET for all participants.

The absolute value, absolute change, and percent change from baseline of plasma PGRN will be presented in data listings by cohort and timepoint for the Full Analysis population. Plasma PGRN concentration data will be summarized by cohort and timepoint for the Full Analysis population using descriptive statistics: number of participants with non-missing data (n), mean, SD, CV, median, minimum, maximum, geometric mean and geometric CV. All plasma PGRN concentration values that are BLQ will be set to $\frac{1}{2}$ the lower limit of quantification (LLOQ) when calculating summary statistics.

Mean (\pm SD) absolute value, absolute change and percent change from baseline in plasma PGRN concentration versus nominal time profiles will be plotted on linear and semilogarithmic scales by cohort for the Full Analysis population. In addition, the absolute value, absolute change and percent change from baseline in plasma PGRN concentration at the individual level versus actual time profiles will be plotted on linear and semilogarithmic scales by cohort for the Full Analysis population.

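### SAP 7.3 drops below-quantification troughs from the Ctrough summary while SAP 7.1 counts the same samples as zero, so Ctrough can only be biased upward and the two tables can disagree

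*SAP*

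**What the plan says.** SAP 7.3 derives three serum parameters: Cmax, Ctrough and an accumulation ratio based on Ctrough (ARCtrough). One BLQ rule covers them all: "all serum concentrations that are BLQ prior to the first measurable concentration will be set to zero and treated as missing thereafter". Ctrough is defined as "Trough serum concentration following each dose (equivalent to the trough concentration prior to each dose", so it is a single measured concentration. The parameters are summarized with "n, arithmetic mean, SD, CV, geometric mean, geometric mean CV, 90% CI, minimum, median, and maximum".

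SAP 7.1 summarizes the serum concentrations themselves by visit and timepoint, for the same PK analysis population. Its rule differs: "All serum concentration values below the limit of quantification (BLQ) will be set to zero when calculating summary statistics". The statistics requested there include "mean, SD, CV, median, minimum, maximum, geometric mean, and geometric CV". Samples are "collected at predose and at the end of infusion (within 15 minutes after the end of infusion) on weeks 1, 2, 5, 9, 13" and later weeks.

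For plasma progranulin (PGRN), SAP 8.1 uses a third rule: "All plasma PGRN concentration values that are BLQ will be set to" half the LLOQ. SAP 8.2 does the same for CSF PGRN.

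Ctrough is a secondary endpoint, listed in SAP 1.1 under "AL001 PK parameters (if data permit"). The protocol has no BLQ rule. Neither document explains why 7.1 and 7.3 differ, and neither asks for a count of BLQ troughs.

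**The concern.** Treating late BLQ values as missing is a convention for integrating a concentration curve, where an isolated BLQ point in the tail should not distort an area. SAP 7.3 derives no area. Its rule falls mainly on Ctrough, where the BLQ value is the result itself and not one point on a curve. The values removed are by definition the lowest ones, so the summary is selected on its own outcome.

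What is at stake is the description of exposure at the end of the dosing interval. Protocol 1.3.2 reports that treated subjects have developed anti-drug antibodies (ADAs) and that their effect with longer exposure is still being assessed. If ADAs lowered exposure in some participants, low or BLQ troughs are where it would show. The Ctrough table would omit those values, and a reader comparing it with the pre-dose rows of the concentration table would find a different n and a different mean without explanation.

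**Working it through.** The plan gives no figure on this point, so there is none to reproduce.

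**Step 1: which samples the rule reaches.** Sampling starts with a pre-dose and an end-of-infusion draw at Week 1 (SAP 7.1, Appendix 14.3). The end-of-infusion sample should be measurable. The zero branch of 7.3 then covers only the Week 1 pre-dose sample, which is not a trough. The first true trough is the Week 5 pre-dose sample. From there on a BLQ trough falls in the missing branch.

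**Step 2: the two tables compared.** Let k of n troughs at a visit be BLQ, with f = k/n, and let S be the sum of the quantifiable values.

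- 7.3 (missing): mean = S/(n − k), on n − k values.
- 7.1 (zero): mean = S/n, on n values.
- Ratio 7.3/7.1 = n/(n − k) = 1/(1 − f), whatever the distribution.

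With n = 20, the ceiling for each mutation cohort in Protocol 4.1:

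| BLQ troughs | f | Ratio 7.3/7.1 | n in 7.3 |
|---|---|---|---|
| 0 | 0% | 1.000 | 20 |
| 1 | 5% | 20/19 = 1.053 | 19 |
| 2 | 10% | 20/18 = 1.111 | 18 |
| 4 | 20% | 20/16 = 1.250 | 16 |

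**Step 3: bias against the uncensored mean.** Every dropped value lies below the LLOQ and every retained value at or above it, so dropping raises both means. Zero lies below the true value, so it lowers the arithmetic mean. A single zero leaves the geometric mean and geometric CV undefined.

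To show size, assume lognormal troughs with the LLOQ at the f-quantile. With s = √ln(1 + CV²) and z = Φ⁻¹(f):

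- Arithmetic mean, missing/true = Φ(s − z)/(1 − f)
- Arithmetic mean, zero/true = Φ(s − z)
- Geometric mean, missing/true = exp[s·φ(z)/(1 − f)]

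For f = 10%, z = −1.282 and φ(z) = 0.1755:

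- CV 30%: s = 0.294, Φ(1.576) = 0.942. Missing gives 0.942/0.9 = 1.047 (arithmetic) and exp(0.294 × 0.1755/0.9) = 1.059 (geometric).
- CV 100%: s = 0.833, Φ(2.115) = 0.983. Missing gives 0.983/0.9 = 1.092 and exp(0.833 × 0.1755/0.9) = 1.176.

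Over CV 30% to 100%:

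| f | Missing, arithmetic | Missing, geometric | Zero, arithmetic | Half LLOQ, arithmetic |
|---|---|---|---|---|
| 5% | +2.5% to +4.6% | +3.2% to +9.5% | −2.6% to −0.7% | −1.2% to −0.2% |
| 10% | +4.7% to +9.2% | +5.9% to +17.6% | −5.8% to −1.7% | −2.5% to −0.5% |
| 20% | +9.0% to +19.1% | +10.8% to +33.8% | −12.8% to −4.7% | −5.3% to −1.2% |

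At f = 10% half the LLOQ lowers the geometric mean by about 5% (CV 30%) to 3% (CV 100%). All values of f and CV here are assumptions.

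The certain direction applies to Ctrough. For ARCtrough a BLQ trough removes the ratio altogether, and the direction depends on which of its two troughs is BLQ.

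**The case against.** **The rules have separate scopes.** One governs concentration summaries and the other the calculation of PK parameters, so both can be run as written. A reader might infer a contradiction that makes the SAP unworkable; the text does not support that. What stands is narrower: two tables can give different results for one sample, without explanation.

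**Nobody drops out.** A reader might infer that participants with fast clearance or ADAs vanish from the PK analysis. They do not. The PK analysis population (SAP 2.3.3) needs one determinable parameter, which Cmax would normally supply. Only that visit's Ctrough value goes, and the sample stays in the 7.1 table, the listings and the individual plots.

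**Not carrying zero into 7.3 is defensible**, because 7.3 asks for geometric means. This is correct, and it is why copying the 7.1 rule would not be a repair.

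**BLQ troughs may be rare.** Protocol 1.2.2.1 reports that in healthy volunteers given a single 60 mg/kg dose plasma PGRN stayed above twice baseline for more than 29 days, longer than the 28-day dosing interval. This is indirect, but the documents offer nothing that points to a BLQ rate of 5% to 20%. Protocol 1.3.2 also reports no identified association of ADAs with PK after short exposure. The ADA route is possible, not shown.

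**No decision hangs on it.** The endpoint is descriptive, without a coverage threshold, and SAP 2 plans no formal significance testing. This bears on severity; it does not make the rule right.

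**Conclusion.** The point holds. Whenever a trough is BLQ, SAP 7.3 overstates mean Ctrough, and SAP 7.1 understates the mean of the same samples and cannot give the geometric mean it requests. The direction for Ctrough rests only on the SAP's definitions and on the first end-of-infusion sample being measurable.

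The size cannot be derived from the documents. At an assumed 10% of troughs BLQ and CV 30% to 100%, the Ctrough arithmetic mean is about 5% to 9% too high and the geometric mean about 6% to 18% too high. At 0% BLQ there is no bias and the tables agree. It would go too far to conclude that trough exposure in this trial is overstated, or that loss of exposure through ADAs is being hidden. Severity is minor.

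**What to change.** Use one BLQ rule in SAP 7.1 and 7.3 for pre-dose serum samples taken after the first dose: set them to half the LLOQ, as 8.1 and 8.2 already do for PGRN. Apply it to Ctrough and ARCtrough. Keep the missing-thereafter clause only for any AUC that is derived; 7.3 lists none, although AUCss remains an endpoint in SAP 1.1. Report the number of BLQ troughs by visit and cohort beside the Ctrough summary. Changing 7.3 alone would not be enough, because 7.1 would still show zero and an undefined geometric mean for the same sample.

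The cost is a sentence in each section and one row in a table; no new data are needed. The downside is that half the LLOQ is a simple imputation with a small residual bias: at 10% BLQ, about −2.5% to −0.5% for the arithmetic mean and −5% to −3% for the geometric mean under the same assumptions. The BLQ count lets a reader judge whether that matters.
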